6.1.2.3 Japanese Subjects (Cohorts 13 to 15)

The MRD part in Japanese subjects will involve dose escalation through 3 cohorts. Subjects will be confined throughout the Treatment Period from Day -1 to Day 29. Healthy Japanese subjects will be randomized to receive a single dose of TAK-071 or matching placebo in a 5:1 ratio, followed by a 7-day washout period and multiple doses (21 oral doses QD) of TAK-071 or placebo. The 7-day washout period in Cohorts 13 to 15 is intended to provide sufficient time to characterize the TAK-071 terminal disposition phase, but it is not expected to result in complete disappearance of TAK-071 from plasma prior to starting repeat dosing on Day 8. Nonetheless, Day 8 trough concentrations are expected to be very low (ie, <5% steady state C_{max}).

PK parameters will include a determination of time to steady-state, potential for accumulation, and time dependency in PK. In addition, data will be compared with data generated in non-Japanese subjects to determine if there are any ethnic differences in human PK.

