It is planned that Cohort 2 plasma samples (post-24 hours) will be analyzed separately and will not comprise part of the dose escalation PK datasets.

For illustration purposes, and based on human PK predictions using animal data, the planned dose escalation in the SRD is as follows: 1, 3, 9, 20, 40, and 50 mg. However, based on emerging safety and PK data from Cohort 1 through 6, 18, and 19, doses of 80, 60, and 40 mg are planned for Cohorts 20 to 22 to understand safety and tolerability of TAK-071+donepezil (10 mg). The TAK-071 plasma exposure following an 80 mg TAK-071 + 10 mg donepezil dose is predicted to be approximately equivalent to 15 mg TAK-071 + 5 mg donepezil in chronic administration in the MRD study, and this dose was well-tolerated in Cohort 12. A dose of 160 mg TAK-071 + 10 mg donepezil will provide an approximate 1.5-fold increase in TAK-071 exposure compared to the 80 mg TAK-071 + 10 mg donepezil dose. The dose selected for Cohort 21 will be not higher than 160 mg and will be based on the safety data from TAK-071 120 mg dose.

It is planned that the MRD cohorts will start no sooner than after all subjects in the SRD Cohort 4 have been dosed. The starting dose of the MRD cohorts will then be decided following a review of the blinded 24-hour safety (AEs, vital signs, ECG, clinical laboratory results) and tolerability from

Cohort 4 and the 24-hour preliminary plasma PK and 12-hour CSF PK data from Cohort 3. Under no circumstances will the starting dose for MRD Cohort 7 exceed that of the immediately preceding cohort for which blinded 24-hour safety and tolerability data have been evaluated and deemed to be acceptable. For example, safety and tolerability data from Cohort 4 would enable a maximum starting MRD dose analogous to Cohort 3. In the unlikely event that CSF concentrations are found to be low, ie, the majority of time points are below the limit of quantification, the MRD start may be postponed until a single dose that provides acceptable CSF concentrations is identified.

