9.1.6 Vital Sign Procedure

In subjects who are not undergoing CSF collection (Cohorts 2, 4 to 8, and 10 to 22), vital signs will include body temperature (oral), respiratory rate, and orthostatic blood pressure and pulse (bpm).

In subjects who have completed enrollment for Cohort 1 at the time of this amendment and in subjects who are undergoing CSF collection (Cohorts 3 and 9), vital signs include body temperature (oral), respiratory rate, supine blood pressure (resting more than 5 minutes), and pulse (bpm).

Vital signs should be collected daily, predose and upon morning rising on days during confinement. In addition, vital signs should be collected in Cohorts 3 and 9 at approximately 5 hour postdose on Day 1 and Day 8 (Cohort 9 only). Vital signs may be repeated. All measurements will be recorded on the source documents and in the eCRF.

When vital signs are scheduled at the same time as blood draws, the blood draw will take priority, and vital signs will be obtained within 0.5 hour before the scheduled blood draw.

For BA/FE Cohort 17, for the fed regimen, if vital signs coincide with a meal, vital signs will take precedence followed by the meal.

For Cohorts 2, 4 to 8, and 10 to 22, orthostatic blood pressure and pulse will be measured at predose and at 2, 4, 6, 8, and 12 hours postdose in the first 24 hours after the initial dose of TAK-071 (Day 1) and then afterwards on days while subjects are in the phase 1 unit. Orthostatic blood pressure will be measured as follows [23]:

1. Have the patient lie down for 5 minutes.
2. Measure blood pressure and pulse rate.
3. Have the patient stand.
4. Repeat blood pressure and pulse rate measurements after standing 1 and 3 minutes.

A drop in bp of ≥ 20 mm Hg, or in diastolic bp of ≥ 10 mm Hg, or experiencing lightheadedness or dizziness is considered abnormal [23].

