(f) Blood and urine samples for clinical laboratory tests (hematology, coagulation, serum chemistry, urinalysis) will be collected as indicated. On Day 1, the urine sample for urinalysis will be taken predose (within 2 hours prior to dosing) and the blood sample for these tests will be taken 1 hour postdose. On subsequent days, blood and urine samples will be taken predose upon rising in the morning under fasted condition.

(g) During the course of the study, regular serum hCG pregnancy tests will be performed for female subjects and subjects will receive continued guidance with respect to the avoidance of pregnancy as part of the study procedures. In addition to a negative serum hCG pregnancy test at Screening, female subjects must have a negative serum hCG pregnancy test at Check-in prior to receiving the first dose of study drug.

(h) FSH concentration will be obtained from postmenopausal women (defined as continuous amenorrhea of at least 2 years and not surgically sterile).

(i) A standard 12-lead ECG will be recorded at Screening, Check-in (Day -1), Day 1 (TAK-071 predose [within 60 minutes prior to dosing] and at 0.5, 1, 2, 4, and 8 hours postdose), Days 2 through 21 (predose), Days 22 and 23 (upon morning rising) or ET. Single ECGs will be taken at all visits.

(j) Continuous 12-lead Holter ECG monitoring will be conducted from 2 hours predose until 24 hours postdose TAK-071 on Day 1 and from 1 hour predose until 48 hours postdose TAK-071 on Day 21.

(k) DIC will be dispensed for treatment

(l) Blood samples for PGx analysis will be collected as follows: 6 mL for DNA on Day 1; 2x2.5 mL for RNA on Day 1 (predose and 12 hours postdose) and 12 hours postdose on Day 21.

(m) Blood samples (3 mL/sample) for plasma measurement of TAK-071 will be collected predose (within 30 minutes prior to dosing) and specified time points outlined in Section 9.1.15.1.

(n) Urine samples for PK analyses will be collected predose within approximately 1 hour of dosing and specified time points outlined in Section 9.1.15.2.

(o) PTEs will be collected from signing of informed consent up until dosing on Day 1.

(p) Any event after dosing on Day 1 will be captured as an AE.

(q) Bowel function will be assessed using the BSF scale and daily stool count.

(r) C-SSRS will be determined as indicated. If clinically significant at Final Visit, C-SSRS will also be determined as part of the Follow-up Visit.

MRD Healthy Volunteer Cohort 9

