- (f) Blood and urine samples for clinical laboratory tests (hematology, coagulation, serum chemistry, urinalysis) will be collected as indicated. On Days -21 to -1, blood and urine samples will be collected on Days -21, -10 and -1. On Day 1, the urine sample for urinalysis will be taken at predose (within 2 hours prior to dosing) and the blood sample for these tests will be taken 1 hour postdose. On subsequent days, blood and urine samples will be taken predose upon rising in the morning under fasted condition.
- (g) During the course of the study, regular serum hCG pregnancy tests will be performed for female subjects and subjects will receive continued guidance with respect to the avoidance of pregnancy as part of the study procedures. In addition to a negative serum hCG pregnancy test at Screening, female subjects must have a negative serum hCG pregnancy test at Check-in (Day -10) prior to receiving the first dose of study drug.
- (h) FSH concentration will be obtained from postmenopausal women (defined as continuous amenorrhea of at least 2 years and not surgically sterile).
- (i) A standard 12-lead ECG will be recorded at Screening, Check-in (Day -22) (donepezil predose [within 60 minutes prior to dosing]), Day -1, Day 1 (TAK-071 predose [within 60 minutes prior to dosing] and at 0.5, 1, 2, 4, and 8 hours postdose), Days 2 to 21 (predose), and Days 22 to 23 (upon morning rising) or ET. Single ECGs will be taken at all visits.
- (j) DIC will be dispensed for treatment
- (k) Donepezil will be given as an oral daily 5 mg tablet in the morning. Subjects will administer donepezil in the morning at home on Days -18 to -11.
- (l) Subjects should be called each outpatient day with a reminder to take their study medication in the morning daily on Days -18 to -11.
- (m) Blood samples for PGx analysis will be collected as follows: 6 mL for DNA predose donepezil on Day -21; 2 \times 2.5 mL for RNA predose donepezil on Day -21, predose TAK-071 on Day 1, and 12 hours postdose on Day 21.
- (n) Blood samples (3 mL/sample collected into EDTA-coated tubes) for plasma measurement of TAK-071 will be collected predose (within 30 minutes prior to dosing) and specified time points outlined in Section 9.1.15.1.
- (o) Blood samples (4 mL/sample collected into sodium heparin tubes) for the measurement of donepezil will be collected predose (within 30 minutes prior to TAK-071 dosing) and specified time points outlined in Section 9.1.15.1.
- (p) CCI

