(i) A standard 12-lead ECG will be recorded at Screening, Check-in (Day -1), Days 1 and 8 (TAK-071 predose [within 60 minutes prior to dosing] and at 0.5, 1, 2, 4, and 8 hours postdose). On the remaining days during confinement 12-lead ECG be recorded (upon morning rising), or ET. Single ECGs will be taken at all visits.

(j) DIC will be dispensed for treatment.

(k) Blood samples for PGx analysis will be collected as follows: 6 mL for DNA on Day 1; 2x2.5 mL for RNA predose TAK-071 on Day 1, predose TAK-071 on Day 8, and 12 hours postdose on Day 28.

(l) Blood samples (3 mL/sample into EDTA coated tubes) for plasma measurement of TAK-071 will be collected predose (within 30 minutes prior to dosing) and specified time points outlined in Section 9.1.15.1.

(m) Urine samples for PK analyses will be collected predose within approximately 1 hour of dosing and specified time points outlined in Section 9.1.15.2.

(n) PTEs will be collected from signing of informed consent up until dosing on Day 1.

(o) Any event after dosing on Day 1 will be captured as an AE.

(p) Bowel function will be assessed using the BSF scale and daily stool count.

(q) C-SSRS will be determined as indicated. If clinically significant at Final Visit, C-SSRS will also be determined as part of the Follow-up Visit.

ET=Early Termination Visit, HBsAg=hepatitis B surface antigen, HCV=hepatitis C virus.

- (a) Only subjects in donepezil run-in period will have these assessments.
- (b) A PK blood sample should be collected at the Early Termination Visit if possible.
- (c) Follow-up will occur by telephone on Day 73 (± 2) unless abnormal clinically significant findings are observed upon discharge. In these cases, subjects must then be brought back to the clinic for re-evaluation per investigator's discretion.
- (d) Vital signs (oral temperature, respiration, pulse, and blood pressure) will be obtained as indicated. In addition, orthostatic blood pressure will be measured at predose and at 2, 4, 6, 8, and 12 hours postdose in the first 24 hours after the initial dose of TAK-071 and then afterwards on Days 2, 11, 20 to 22, 41 to 43, 52, and 61 to 63 (upon morning rising or arrival for outpatient visit) or ET as detailed in Section 9.1.6.
- (e) Height and BMI will be collected at Screening only.
- (f) All ongoing medications will be recorded from Screening and throughout the study.

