- (g) Blood and urine samples for clinical laboratory tests (hematology, coagulation, serum chemistry, urinalysis) will be collected as indicated. On Days 1 and 42, the urine sample for urinalysis will be taken at predose (within 2 hours prior to dosing) and the blood sample for these tests will be taken 1 hour postdose. On all other days, when the subjects are confined at the phase 1 unit, blood and urine samples will be taken predose upon rising in the morning under fasted condition.
- (h) FSH concentration will be obtained from postmenopausal women (defined as continuous amenorrhea of at least 2 years and not surgically sterile). The result must be >40 IU/L for the subject to be enrolled.
- (i) A standard 12-lead ECG will be recorded at Screening, Check-in (Day -1), Days 1, 21, 42, and 62 (TAK-071 predose [within 60 minutes prior to dosing] and at 0.5, 1, 2, 4, and 8 hours postdose), Days 2, 11, 20 to 22, 41 to 43, 52, and 61 to 63 (upon morning rising or arrival for outpatient visit) or ET. Single ECGs will be taken at all visits.
- (j) DIC will be dispensed for treatment.
- (k) Subjects must be receiving ongoing donepezil therapy (10 mg) in the evening for a minimum of 21 days prior to Check-in and during the study (if subjects were receiving 5 mg dose at Screening, it should be up-titrated to 10 mg on Day -21). Alternatively, subjects may be diagnosed at Screening and start donepezil run-in for 49 days prior to Day -1, and on stable 10 mg dose of donepezil 21 days prior to Day -1. Subjects will continue with their donepezil therapy during the TAK-071 Treatment Period.
- (l) Blood samples for PGx analysis will be collected as follows: 6 mL for DNA on Day 1; 2×2.5 mL for RNA predose TAK-071 on Days 1 and 42 and 12 hours postdose on Days 21 and 62.
- (m) Blood samples (3 mL/sample into EDTA coated tubes) for plasma measurement of TAK-071 will be collected predose (within 30 minutes prior to dosing) and specified time points outlined in Section 9.1.15.1.
- (n) Blood samples (4 mL/sample collected into sodium heparin tubes) for the measurement of donepezil will be collected predose (within 30 minutes prior to TAK-071 dosing) and specified time points outlined in Section 9.1.15.1.
- (o) Urine samples for PK analyses will be collected predose within approximately 1 hour of dosing and specified time points outlined in Section 9.1.15.2.

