For ECG interpretation data, shift tables will be provided by visit for the number of subjects with each interpretation by the interpretation at baseline.

All other ECG data will be presented in data listings.

Dates and times for the start and stop of continuous 12-lead Holter ECG monitoring will be presented in a data listing. The Holter ECG recordings will be stored, and no data will be extracted for summary and analysis during the conduct of this study.

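### In multiple-dose Cohorts 7 to 15 the scheduled ECG series and postdose blood-pressure readings follow only a first dose, so the ECG and vital-sign endpoints do not sample the steady-state peak

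*Protocol*

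**What the plan says.** Timing of the scheduled safety assessments in the multiple-rising-dose (MRD) cohorts:

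- **Cohorts 7 and 8** (Protocol Appendix A, ECG footnote): single 12-lead ECGs at 0.5, 1, 2, 4 and 8 h after dosing on Day 1, then "Days 2 through 21 (predose), Days 22 and 23 (upon morning rising) or ET".
- **Cohorts 10 to 12** (same appendix): the same Day 1 series, then "Days 2 to 21 (predose), and Days 22 to 23 (upon morning rising) or ET".
- **Cohorts 9 and 13 to 15**: the series on Days 1 and 8. For Cohorts 13 to 15 the footnote continues: "On the remaining days during confinement 12-lead ECG be recorded (upon morning rising), or ET". Cohort 9 is equivalent. Day 8 is the first daily dose after the washout, and Protocol 6.1.2.3 says of it: "Nonetheless, Day 8 trough concentrations are expected to be very low", meaning below 5% of steady-state Cmax. Protocol 6.1.2.1 says the same for Cohort 9.
- **Blood pressure** (Protocol 9.1.6): orthostatic readings at 2, 4, 6, 8 and 12 h follow the initial TAK-071 dose only. Otherwise: "Vital signs should be collected daily, predose and upon morning rising on days during confinement". Cohort 9 has supine readings, with one at about 5 h on Days 1 and 8.
- **Holter** (Protocol 9.1.12.2, Table 9.b): Cohorts 7 and 8 are also recorded to 48 h after the Day 21 dose and Cohort 9 to 48 h after the Day 28 dose, with triplicates extracted before each PK draw from 0.5 h. Cohorts 10 to 15 are not listed. SAP 7.12.4 states: "The Holter ECG recordings will be stored, and no data will be extracted for summary and analysis during the conduct of this study".
- **Cohort 16**, by contrast, has the ECG series on "Days 1, 21, 42, and 62 (TAK-071 predose [within 60 minutes prior to dosing] and at 0.5, 1, 2, 4, and 8 hours postdose", which includes the last dosing day of each period.

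SAP 7.12.3 and 7.12.4 repeat the MRD times. The primary ECG and vital-sign endpoints (Protocol 5.2.1.1) count subjects with one or more postdose markedly abnormal values (MAVs).

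**The concern.** The MRD part is there to characterise safety on repeated dosing, and TAK-071 accumulates on daily dosing. With this schedule the MAV percentages rest on dense readings at first-dose exposure and on trough-type readings afterwards.

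The gap matters most in Cohorts 10 to 12. Protocol 6.2.2.4 times donepezil so that both drugs peak together and any interaction has the best chance of showing. Protocol 4.3 anticipates possible synergy and makes review of these cohorts a precondition for dosing patients. PK is drawn serially on Day 21, but no ECG or blood-pressure series accompanies it. A transient effect at the combined peak on repeated dosing would not be recorded by any scheduled reading in healthy subjects.

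**Working it through.** The plan gives no figure to reproduce here. The check is a comparison of schedules plus a model to size what is missed. The Appendix A grids for Cohorts 7, 8 and 10 to 16 are not in the available text, so their footnotes and the SAP were used.

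**Schedule count.** In Cohorts 7, 8 and 10 to 12, scheduled ECGs after the first TAK-071 dose number 5 (Day 1 series) + 20 (Days 2 to 21, predose) + 2 (Days 22 and 23, roughly 24 and 48 h after the last dose) = 27. The 5 taken within hours of a dose all follow the first dose. After a steady-state dose, Cohorts 7 to 15 have 0 safety ECG series and 0 blood-pressure series.

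**Who has Holter after the last dose.** Cohorts 7 to 9: 3 × 6 = 18 active subjects, with 12 postdose extraction times on Day 21 (13 on Day 28 in Cohort 9, which adds 36 h). Cohorts 10 to 15: 3 × 6 + 3 × 5 = 33 active subjects, none.

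**Size (assumed model).** One compartment, oral, linear kinetics, 21 doses 24 h apart:

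C(t) = ka/(ka − k) × (e^(−kt) − e^(−ka·t)), with k = ln 2 / half-life and ka solved so that ln(ka/k)/(ka − k) = 4 h.

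The 4 h tmax comes from Protocol 6.2.2.4. The half-lives of 65 and 140 h are the thresholds in Protocol 6.2.2.2 for shortening or extending dosing; they are not observed values. 100 h is an intermediate point. Doses are superposed.

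| Half-life (h) | Last-dose peak ÷ first-dose peak | Predose on last dosing day ÷ following peak | Day 8 residual ÷ steady-state peak |
|---|---|---|---|
| 65 | 4.47 | 0.803 | 3.9% |
| 100 | 6.39 | 0.862 | 5.1% |
| 140 | 8.25 | 0.892 | 5.4% |

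The last column is close to the protocol's own expectation of under 5%, so the model is not out of line with the plan. It also means that the Day 8 ECG series is taken at nearly first-dose exposure. The part of steady-state exposure above the predose level is 1 − 0.892 = 0.108 to 1 − 0.803 = 0.197, roughly the top 11-20%.

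**Do the single-dose combination cohorts fill the gap?** In Cohorts 20 to 22 the ECG series is on Day 1 and donepezil is given about 24 h later. ECGs on Days 2 to 5 are on morning rising, and the orthostatic series lies in the first 24 h after TAK-071. So no ECG series follows donepezil there.

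**The case against.** Several points on the other side are sound.

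- A reader might infer that no MRD subject has a postdose ECG at steady state. That is not so: Cohorts 7 to 9 have Holter recordings across the last-dose peak, and Protocol 9.1.12 plans central retrospective review, earlier if safety information warrants. What stands is that the SAP leaves these data out of this study's summaries and that Cohorts 10 to 15 have no such recordings.
- A reader might divide 80 by 15, because Protocol 6.2.2.2 has 80 mg single-dose exposure "predicted to be approximately equivalent to 15 mg TAK-071 + 5 mg donepezil in chronic administration", and infer 5.3-fold accumulation with first-dose readings at 19% of steady state. That requires dose-proportional exposure. The same section predicts only about 1.5-fold more exposure at 160 mg than at 80 mg, so neither figure is supported.
- Daily predose readings already see about 80-89% of the peak under the model. This limits the size of the gap and stands in full.
- Protocol 9.1 allows safety times to be moved nearer to peak, and SAP 7.12.3 and 7.12.4 count unscheduled readings in the MAV tables. A peak reading would therefore count if someone took one. But this is a permission, and nothing schedules it.
- High single doses, such as the planned 120 mg in Cohort 18 and 80 mg in Cohort 20, have full ECG and orthostatic series, so high TAK-071 exposure without donepezil is sampled. Cohorts 10 to 12 also have a Day 1 series on steady-state donepezil. Neither covers accumulated TAK-071 together with the donepezil peak.

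**Conclusion.** The point holds as a gap in scheduling; the documents do not contradict themselves. In Cohorts 7 to 15 no scheduled safety ECG series and no scheduled postdose blood-pressure reading falls near the steady-state peak, and the Holter data that do cover it in Cohorts 7 to 9 are outside the SAP's summaries. The primary MAV percentages for ECG and vital signs therefore describe first-dose peaks and later troughs.

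Under the assumed model the last-dose peak is about 4.5 to 8 times the first-dose peak, and roughly the top 11-20% of steady-state exposure goes unsampled. Both ranges rest on linear one-compartment kinetics, a 4 h tmax, and half-lives taken from decision thresholds. The gap is moderate because trough readings see most of the exposure, and it is most consequential in the combination Cohorts 10 to 12. It should be addressed because the remedy is cheap and Cohort 16 shows that it is feasible.

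**What to change.** **Subjects not yet dosed and any added MRD cohort.** Schedule the 0.5-8 h ECG series and the 2-12 h orthostatic series (the 5 h supine vital signs in Cohort 9) on the last dosing day, Day 21 or 28. Subjects are then confined and serial PK is already drawn. Align SAP 7.12.3 and 7.12.4. In Cohorts 9 and 13 to 15 the ECG series can be moved from Day 8 or added to it. Adding costs about 5 ECGs and, where orthostatic readings apply, 5 orthostatic sets per subject; moving the ECGs adds none but reduces monitoring at the start of daily dosing. The scope may be small: Protocol 6.2.2.2 already reports tolerability from Cohort 12.

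**Completed Cohorts 7 to 9.** Report the Day 21 or 28 Holter extractions in a separate table labelled Holter-derived. Do not merge them into the safety-ECG MAV table: triplicates at 12 or 13 extra times would give these subjects more chances of an abnormal value than others in the same part, and the Holter baseline is defined differently. The cost is earlier reading of recordings already made.

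**Completed Cohorts 10 to 15.** State beside the ECG and vital-sign MAV tables that the steady-state peak was not sampled. The vital-sign tables need the same note for Cohorts 7 to 9, since Holter gives no blood pressure. This costs only wording.
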